9 SAFETY

The analysis population used for safety analyses will be the Safety population. Safety will be assessed on the basis of AE, clinical laboratory data, vital signs, ECG parameters, MMSE and physical examinations.

9.1 ADVERSE EVENTS

All subjects in the Safety population will be included in the adverse event analysis.

AEs will be coded using the Medical Dictionary for Regulatory Activities (MedDRA) coding dictionary (Version 19.1 or higher)

An AE is defined as any untoward medical occurrence in a subject administered a medicinal product and which does not necessarily have to have a causal relationship with this treatment. An adverse event can therefore be any unfavorable and unintended sign symptom (for example, an abnormal laboratory finding), or disease temporally associated with the use of a medicinal product, whether or not considered related to this medicinal product. In clinical studies, an AE can include an undesirable medical condition occurring at any time, including baseline or washout periods, even if no study treatment has been administered.

In this study, all AEs that occur after any subject has been screened through the post-treatment follow-up period, whether or not they are related to the study, must be recorded on the eCRF, and must include the following: date and time of onset, date and time of resolution, severity, seriousness, causality (relationship to study medication), actions required, and outcome. Clinically significant and severe AEs must be examined to determine whether they meet criteria of a dose-limiting toxicity.

A treatment-emergent AE (TEAE) is any that is new in onset or was aggravated in severity or frequency following the first dose of study drug, up to and including the last visit of the study. Treatment emergence will be determined by comparing the AE start date/time with the actual date/time of first dose. In the case that the AE start date/time are incomplete, treatment emergence will be imputed according to the algorithm in SAP Section 6.5.

Adverse events will be listed chronologically by cohort/treatment, subject and AE start date/time. This listing will include all data collected in the eCRF, along with the derived variables: onset time since first dose, duration of AE and the coded variables system organ class (SOC) and preferred term (PT). Time since dose and duration will be calculated as described in SAP Section 6.3. In addition, serious AEs (SAEs) will be listed separately, if any occurs.

The summary of AEs will be limited to TEAEs only. In cases where severity is missing for a TEAE, the TEAE will be considered to be the highest degree of severity: Severe. In cases where relationship information is missing for a TEAE, the TEAE will be considered to be reasonably related. Displays of TEAEs will include:

- Overall Summary of TEAEs

This table will include the number of events, number and percent of subjects who experienced TEAEs, serious TEAEs, severe TEAEs, related TEAEs and TEAEs leading to study discontinuation, summarized by treatment group.

- Summary of TEAEs by SOC, PT and Treatment Group

A summary of the number of events, number and percent of subjects who experienced at least one TEAE, as well as the number of events, number and percent of subjects who experienced each specific SOC, and PT will be presented by treatment group (including pooled placebo and pooled RP3128). If a subject has more than one occurrence of the same PT then the PT will be counted only once for that subject under the SOC at which it was experienced.

- Summary of TEAEs by SOC, PT, Treatment Group and Maximum Severity

A summary of the number and percent of subjects who experienced at least one TEAE by maximum severity as well as the number and percent of subjects who experienced each specific SOC and PT by maximum severity will be presented by treatment group. For this analysis, if a subject has more than one occurrence of the same PT, then the PT will be counted only once for that subject under the maximum severity at which it was experienced.

- Summary of TEAEs by SOC, PT, Treatment Group and Maximum Relationship

A summary of the number and percent of subjects who experienced at least one TEAE by maximum relationship as well as the number and percent of subjects who experienced each specific SOC and PT by maximum relationship will be presented by treatment group. For this analysis, if a subject has more than one occurrence of the same PT, then the PT will be counted only once for that subject under the maximum relationship at which it was experienced.

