6.3 ATTRIBUTION OF TREATMENT-EMERGENT AE FOR INCOMPLETED AE DATE/TIME

AEs with incomplete start dates and times will be attributed to treatment according to the following algorithm:

1. Only the year is reported: If the year is after the year of the dose, the event will be considered as treatment-emergent. If the year is the same as the day of the dose, the event will not be considered as treatment-emergent.

2. Only the month and year are reported: If the month is after the month of the first dose, event will be considered as treatment-emergent. If the month is the same as the month of the first dose, the event will not be considered as treatment-emergent.
3. Only the time is missing: If the event occurred on or after the day of the first dose in the treatment period, then the event will be considered as treatment-emergent. Otherwise, the event will not be considered as treatment-emergent.

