APPENDIX C: PART 2 (MAD) — SCHEDULE OF EVENTS

Study Day	Screening	Assessment period														
		Admission		CPU Confinement							Discharge	Ambulatory visits				
Study Day	-60 to -1	-1	1	2	3	4	5	6	7	8	9	10	11	12	13	15 (±1) EOS ¹⁸
Confinement ¹	-	X	X	X	X	X	X	X	X	-	-	-	-	-	-	-
Ambulatory visits ²	-	-	-	-	-	-	-	-	-	-	X	X	X	X	X	X
Informed consent ³	X	-	-	-	-	-	-	-	-	-	-	-	-	-	-	-
Medical history ⁴	X	X	-	-	-	-	-	-	-	-	X	-	X	-	-	X
Demographics ⁵	X	-	-	-	-	-	-	-	-	-	-	-	-	-	-	-
Physical examination ⁶	X	X	-	-	-	X	-	-	-	X	-	-	-	-	-	X
Vital signs ⁷	X	X	X	X	X	X	X	X	X	X	X	-	X	-	-	X
Eligibility assessment	X	X	-	-	-	-	-	-	-	-	-	-	-	-	-	-
12-lead ECG ⁸	X	X	X	X	-	-	X	-	X	X	-	-	-	-	-	X
Clinical laboratory ⁹	X	X	-	X	-	-	X	-	X	X	-	-	-	-	-	X
Drug and alcohol screen ¹⁰	X	X	-	-	-	-	-	-	-	-	-	-	-	-	-	-
HbsAg, HCV, HIV	X	-	-	-	-	-	-	-	-	-	-	-	-	-	-	-
Tuberculin test / QuantiFERON-TB®-Gold test	X	-	-	-	-	-	-	-	-	-	-	-	-	-	-	-
EEG ¹¹	-	-	-	-	-	-	-	-	-	-	-	-	-	-	-	-
Randomization	-	-	X	-	-	-	-	-	-	-	-	-	-	-	-	-
Pregnancy test (female) ¹²	X	X	-	-	-	-	-	-	-	-	-	-	-	-	-	-

Cognitive test (e.g. MMSE)	X	-	-	-	-	-	-	-	-	X	-	-	-	-	-	-
Study drug dispensing ¹³	-	-	X	X	X	X	X	X	X	-	-	-	-	-	-	-
Study drug administration ¹⁴	-	-	X	X	X	X	X	X	X	-	-	-	-	-	-	-
PK sampling blood ¹⁵	-	-	X	X	X	-	X	-	X	X	X	X	X	X	X	X
Biomarkers ¹⁶	-	-	X	-	-	-	-	-	X	-	-	-	-	-	-	-
Adverse events ¹⁷	X	X	X	X	X	X	X	X	X	X	X	X	X	X	X	X
Concomitant medication	X	X	X	X	X	X	X	X	X	X	X	X	X	X	X	X

Foot notes:

1. CPU confinement: Subjects will enter the CPU on Day -1 (afternoon) and will be discharged on day 8 after safety assessment.
2. Ambulatory visit: Day 9, Day 10, Day 11, Day 12, Day 13 and Day 15.
3. The screening assessments will be performed ≤ 60 days prior to initiation of treatment and informed consent will be obtained prior to initiating any study procedures.
4. Detailed history will be taken at screening this include present history, past history, allergy, family history, concomitant medication and prior medication (in last 8 weeks); and other medical history. Abbreviated history will be taken at all subsequent visits.
5. Demographic will age, sex and race.
6. Physical examination includes local and systemic examination and measuring height and weight. Detailed examination will be performed at screening, Day -1, Day 4, Day 8 and Day 15. At other time point, examination will be done as clinically indicated. Height will only be measured at screening.

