CFB ¹ Day 7 (4 hr Post-dose)	Overall	xxx						x.xxxx	x.xxxx
	Placebo	xxx	x.xxx	x.xxx					
	RP3128	xxx	x.xxx	x.xxx	x.xxx	x.xxx	x.xxx, x.xxx	x.xxxx	
CFB ² Day 7(4 hr Post dose)	...								

Note: 1 Baseline set at Day 1 pre-dose
 2 Baseline set at Day 7 pre-dose
 LSMeans: Least square means; Std Err: Standard error
 LSMeans, Std Err, 95% confidence intervals and p-values are based on an ANCOVA with change from baseline as dependent variable, visit and treatment as fixed effect and baseline as covariate. P-values are from two-sided test at 5%-level.

Data source: Listings 16.2.6.1

Programming note: Replace <expression value> with Th1, Th2, and Th17 and X will be assigned as 1, 2, and 3 for expression Th1, Th2 and Th17 respectively

**Table 14.3.1.1.S/M Treatment-Emergent Adverse Events – Overall Summary (SAD/MAD)
Safety Population**

	Treatment at Onset of Adverse Event						
	Pooled Placebo (N=xx)	RP3128 25 mg (N=xx)	RP3128 50 mg (N=xx)	RP3128 100 mg (N=xx)	RP3128 200 mg (N=xx)	RP3128 400 mg (N=xx)	RP3128 Overall (N=xx)
Number (%) of Subjects with TEAE	xx (xx.x%) [xx]	xx (xx.x%) [xx]	xx (xx.x%) [xx]	xx (xx.x%) [xx]	xx (xx.x%) [xx]	xx (xx.x%) [xx]	xx (xx.x%) [xx]
Number (%) of Subjects with Serious TEAE	xx (xx.x%) [xx]	xx (xx.x%) [xx]	xx (xx.x%) [xx]	xx (xx.x%) [xx]	xx (xx.x%) [xx]	xx (xx.x%) [xx]	xx (xx.x%) [xx]
Number (%) of Subjects with Severe TEAE	xx (xx.x%) [xx]	xx (xx.x%) [xx]	xx (xx.x%) [xx]	xx (xx.x%) [xx]	xx (xx.x%) [xx]	xx (xx.x%) [xx]	xx (xx.x%) [xx]
Number (%) of Subjects with Related TEAE	xx (xx.x%) [xx]	xx (xx.x%) [xx]	xx (xx.x%) [xx]	xx (xx.x%) [xx]	xx (xx.x%) [xx]	xx (xx.x%) [xx]	xx (xx.x%) [xx]
Number (%) of Subjects with Study Discontinued due to TEAE	xx (xx.x%) [xx]	xx (xx.x%) [xx]	xx (xx.x%) [xx]	xx (xx.x%) [xx]	xx (xx.x%) [xx]	xx (xx.x%) [xx]	xx (xx.x%) [xx]

Notes: A treatment-emergent adverse event (TEAE) is an AE, which starts or worsens after treatment with the study drug.
 An AE is considered to be related if it is reasonably related to study treatment.
 Summaries are presented as: number of subjects (percentage of subjects) [number of events]

**Table 14.3.1.2.S/M Treatment-Emergent Adverse Events by System Organ Class and Preferred Term (SAD/MAD)
Safety Population**

System Organ Class/ Preferred Term	Treatment at Onset of Adverse Event						
	Pooled Placebo (N=xx)	RP3128 25 mg (N=xx)	RP3128 50 mg (N=xx)	RP3128 100 mg (N=xx)	RP3128 200 mg (N=xx)	RP3128 400 mg (N=xx)	RP3128 Overall (N=xx)
Any System Organ Class							

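### The rule that flags treatment-emergent AEs tests only the start date, so it does not carry out the worsening half of the SAP's own definition

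*SAP*

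**What the plan says.** Section 4.1 lists the incidence of AEs first among the primary endpoints. Section 9.1 gives this meaning to the term treatment-emergent AE: it "is any that is new in onset or was aggravated in severity or frequency following the first dose of study drug". The definition has two limbs: onset after dosing, and worsening after dosing.

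The next sentence gives the derivation: "Treatment emergence will be determined by comparing the AE start date/time with the actual date/time of first dose". For incomplete dates it refers to an algorithm, which is found in Section 6.3: "AEs with incomplete start dates and times will be attributed to treatment according to the following algorithm". All three branches of that algorithm look at when the event started. For example, the branch for a known date without a clock time reads: "If the event occurred on or after the day of the first dose in the treatment period, then the event will be considered as treatment-emergent". An earlier date means that the event is not flagged.

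Section 9.1 also restricts the tables: "The summary of AEs will be limited to TEAEs only". The footnotes of the four TEAE shells repeat the two-limbed definition, in Table 14.3.1.1 as "A treatment-emergent adverse event (TEAE) is an AE, which starts or worsens after treatment with the study drug".

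Pre-dose events are in the data, because Section 9.1 requires recording of "all AEs that occur after any subject has been screened through the post-treatment follow-up period". For the MAD part, Appendix C states: "The screening assessments will be performed ≤ 60 days prior to initiation of treatment". For SAD, the schedule-of-events footnotes put consent no more than 28 days before treatment.

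**The concern.** A comparison of start date with dose date can test only the first limb. Nothing in Section 9.1 or 6.3 compares severity or frequency before and after dosing, so a programmer who codes the flag as written leaves out the worsening limb.

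The event type at risk is narrow but relevant in a first safety study: an AE already present at dosing that becomes worse on drug. Such an event may be severe, judged related, or lead to discontinuation, and under the coded rule it would be absent from those rows as well. The tables would then carry a footnote describing a wider set of events than they contain. Measured against the SAP's definition, the rule can only remove events, never add them. That runs against the cautious approach elsewhere in Section 9.1, where missing severity is set to the highest degree and missing relationship is set to related.

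**Working it through.** The SAP gives no figure to reproduce here. The check applies the definition and the rule to each possible AE pattern.

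| AE pattern | Definition (9.1, shell footnotes) | Start-date rule (9.1, 6.3) | Agreement |
|---|---|---|---|
| Starts after first dose | TEAE | TEAE | yes |
| Starts before first dose, unchanged | not TEAE | not TEAE | yes |
| Starts before first dose, more severe afterwards | TEAE | not TEAE | **no** |
| Starts before first dose, more frequent afterwards | TEAE | not TEAE | **no** |

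**Where the conflicting events go.** The summaries are limited to TEAEs, so the last two patterns are missing from Tables 14.3.1.1 to 14.3.1.4. They remain in Listing 16.2.7.1, which covers all AEs and has a TEAE column, and in Listing 16.2.7.2 if serious.

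**Which events can be affected.** Section 9.5 sends significant findings present before consent to the medical history form. If such a condition worsens after dosing and is entered as a new AE, its start is post-dose and the rule catches it. The gap is therefore AEs with onset between screening and first dose that are still present at dosing and then worsen.

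**What the AE record holds.** The data items in Section 9.1 and the columns of Listing 16.2.7.1 show one onset, one resolution and one severity per AE. Frequency is not among them, although the definition relies on it.

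**Size of one affected subject.** Group sizes are from the cohort tables in Section 3.6, assuming that all randomized subjects are dosed.

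- SAD 25 mg: 1/3 = 33.3 percentage points
- SAD 50 mg and 100 mg: 1/4 = 25.0 points
- SAD 200 mg and 400 mg, and each MAD dose: 1/6 = 16.7 points
- SAD RP3128 overall: 3 + 4 + 4 + 6 + 6 = 23, so 1/23 = 4.3 points
- MAD RP3128 overall: 6 + 6 + 6 = 18, so 1/18 = 5.6 points
- SAD pooled placebo: 1 + 2 + 2 + 2 + 2 = 9, so 1/9 = 11.1 points
- MAD pooled placebo: 2 + 2 + 2 = 6, so 1/6 = 16.7 points

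These shifts apply to a preferred-term row only if the subject has no other TEAE of that term. They apply to the any-TEAE row only if the subject has no other TEAE at all.

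**The case against.** The strongest reply is that no event need be lost. If sites enter a post-dose worsening as a new AE with its own start, the start-date rule implements the definition. That convention would normally sit in the eCRF completion guidelines, which Section 2 names among the documents reviewed and which are not available here. Some of the SAP's text would fit it: each record has one severity, and the maximum-severity table expects several occurrences of the same preferred term in one subject. This part of the reply stands. The documents do not show that any event will be lost. They show that the SAP depends on a convention it neither states nor cites.

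Exposure is also limited. These are healthy volunteers, eligibility is assessed again on Day -1 in MAD, and 60 days is the longest MAD screening window, not a typical one. That makes the event type uncommon, but it does not reconcile the rule with the definition.

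A reader might infer more than the text supports:

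- That worsened events vanish from all AE output. They do not; the listings keep them.
- That the comparison of active drug with placebo is biased in a known direction. The same rule applies to pooled placebo, so no direction follows.
- That the any-TEAE incidence must move by 17 to 33 points per affected subject. It moves only for a subject with no other TEAE.

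**Conclusion.** The contradiction stands. Section 9.1 and the shell footnotes count AEs that worsen after dosing; the derivation in 9.1 and the algorithm in 6.3 cannot identify them from the start date. The SAP states both the definition and the rule, so this is an inconsistency in the SAP and not a detail left to the protocol.

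The consequence is conditional. Events drop out of the four TEAE summaries only if a worsening stays on the original record, and how many would do so cannot be derived from the SAP. Where it happens, a single subject is visible in arms of 3 to 6. The point deserves correction before unblinding because it concerns the classification behind the first primary endpoint and is cheap to settle. It does not call the design or the safety conclusions into question.

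**What to change.** 1. In Section 9.1, and consistently in Section 6.3, flag an AE as treatment-emergent if it starts on or after the first dose, or if it started before the first dose and its recorded severity (or frequency, where recorded) increased afterwards. If frequency is not collected, say that this limb is assessed only where the information exists.
2. State one recording convention. If a worsening is a new linked record with its own start, flag only that record. If it stays on the original record, flag that record. Count the event once either way; flagging both would inflate the event counts in Tables 14.3.1.1 and 14.3.1.2.
3. Before unblinding, review every AE with pre-dose onset for later worsening and set the flag accordingly.
4. Correct the cross-reference in Section 9.1: the incomplete-date algorithm is in Section 6.3, not 6.5. The pointer to 6.3 for onset time and duration in the same section should likewise go to 6.2.

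The cost is a few sentences of SAP text, one extra condition in the TEAE flag and a small blinded review. TEAE incidence may come out slightly higher. The shell footnotes need no change.

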9.2 LABORATORY EVALUATIONS

All subjects in the Safety population will be included in the safety laboratory analysis.

9.2.1 Collection Schedule

At screening, Serology, Tuberculin test / QuantiFeron- TB®-Gold test, Alcohol and urine drug screening will be done to assess eligibility for the study. Drug screening includes opiates, methadone, cocaine, amphetamine, cannabinoids, barbiturates, and benzodiazepines. Alcohol will be screened using alcohol breath test. If the subject has a positive result, the subject will be considered a screen failure and must be excluded from the study. The result will be listed by cohort/treatment, subject and visit.

Female subjects will undergo a serum pregnancy test (quantitative β -HCG) test at screening.

UPT (Urine pregnancy tests) will be performed at later time points in case of suspected pregnancy. The result will be listed by cohort/treatment, subject and visit.

Follicular Stimulating Hormone (FSH) will be evaluated at screening to confirm post-menopausal status for the females who reported having no menses less than 12 months.

For SAD part, the clinical laboratory evaluations, including Clinical chemistry, hematology, serum electrolyte, coagulation and urinalysis, will be performed at screening, Day -1, Day 2, Day 3, Day 8 and Day 15. For MAD part, the clinical laboratory evaluations, including Clinical chemistry, hematology, serum electrolyte, coagulation and urinalysis, will be performed at screening, Day -1, Day 2, Day 5, Day 7, Day 8 and Day 15. If blood, nitrites or leukocytes are abnormal, automatically microscopic urinalysis will be performed. Additional investigations will be performed if clinically indicated.

Laboratory assessment times are shown below in Table 3.

Table 3. Laboratory Parameters Assessment Times

Visit/Day	Clinical Laboratory	Serology	FSH	Drug and alcohol screen	Pregnancy testing
Screening	✓	✓	✓	✓	✓
Day -1 (Check-in)	✓			✓	✓
Day 2	✓				
Day 3	✓(SAD)				
Day 5	✓(MAD)				
Day 7	✓(MAD)				
Day 8	✓				
Day 15	✓				

9.2.2 Derived and Imputed Data

Some numeric lab values may be reported as '>n.n' or '<n.n'; these will be analyzed in the summary statistics as n.n. For example, potassium recorded as >9.0 mmol/L would be summarized as 9.0 mmol/L.

Baseline is defined as the last non-missing observation prior to first dosing on Day 1.

9.2.3 Data Summarization and Presentation

Laboratory sample data and values from laboratory assessments will be listed chronologically by cohort/treatment, subject, and visit. Abnormal findings in laboratory data will be listed with a flag for clinical significance based on investigator judgment. Abnormal laboratory findings will also be provided in a separate listing.

For quantitative data, change-from-baseline (CFB) will be calculated as the difference between the post-dose visit and baseline. For the SAD part, CFB will be calculated for Day 2, Day 3 (at discharge), Day 8, and Day 15. For the MAD part, CFB will be calculated for Day 2, Day 5, Day 7, Day 8 (at discharge), and Day 15.

The laboratory will assign a reference range indicator to all test results by comparing the actual test value to the reference range. The quantitative results will have indicator values of Low, High, and Normal, while the qualitative results will have indicator values of Normal and Abnormal. . The investigator or designee will review non-normal results to judge their clinical significance.

Quantitative results will be summarized for baseline, post-dose visits and CFB values by treatment group using standard summary statistics (n, mean, SD, minimum, median and maximum). Qualitative results (e.g., some tests in urinalysis) will be summarized by treatment group using frequency and percentage. The reference range indicator data will also be tabulated using frequency and percentage for both quantitative and qualitative results. No inferential tests will be conducted on lab data.

In addition, 3 by 3 shift tables will be produced to compare the change in reference range indicator from baseline to Day 3 for the SAD / Day 8 for the MAD part for each laboratory test. For parameters where only two possible values are available (i.e., Normal and Abnormal), the Abnormal values will be counted as High (H) in the 3 by 3 table.

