6 GENERAL ASPECTS FOR STATISTICAL ANALYSIS

6.1 SUMMARY STATISTICS

The standard summary statistics that will be calculated for quantitative and qualitative variables are:

- Quantitative:
 - Standard Statistics for both Safety/PK: Number of subjects, mean, median, standard deviation (SD), minimum and maximum of the raw data
 - Additional Statistics for PK: coefficient of variance (PK concentration and PK parameters), geometric mean, and geometric CV (%) (PK parameters AUC and C_{max} in SAD part and AUC₀₋₂₄, C_{max}, C_{min}, C_{trough} in MAD part)
- Qualitative: number of subjects (n), number of missing observations (nmiss), absolute and relative frequencies (%) per category.

Demographics and disposition will be summarized by treatment group and overall.

Data collected pre- and post-dose during the treatment period (e.g., vital signs, ECG, and clinical laboratory) will be summarized by treatment group (dose level), visit and/or time point. For quantitative variables (ECG measurements, vital signs, hematology, etc.), change from baseline will be calculated and summarized by treatment, visit and/or time point together with baseline and post-dose value. For qualitative variables (e.g., ECG interpretation, urinalysis), standard summary of frequencies will be calculated by treatment, visit and/or time points. For safety lab data only, shift table will be produced to present the change of reference range indicator from baseline to post-dose. PK parameters will be summarized by treatment group, and visit (if applicable). All subjects assigned and treated with Placebo in different cohorts will be pooled together and summarized as a single group.

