		xx (xx.x%)	xx (xx.x%)	xx (xx.x%)	xx (xx.x%)	xx (xx.x%)	xx (xx.x%)
		xx (xx.x%)	xx (xx.x%)	xx (xx.x%)	xx (xx.x%)	xx (xx.x%)	xx (xx.x%)
		Relation to Reference Range, n (%)					
		n	n	n	n	n	n
		xx (xx.x%)	xx (xx.x%)	xx (xx.x%)	xx (xx.x%)	xx (xx.x%)	xx (xx.x%)
		xx (xx.x%)	xx (xx.x%)	xx (xx.x%)	xx (xx.x%)	xx (xx.x%)	xx (xx.x%)
		xx (xx.x%)	xx (xx.x%)	xx (xx.x%)	xx (xx.x%)	xx (xx.x%)	xx (xx.x%)
	Day X
	Follow-up or ET
						

*Baseline is defined as the last observation prior to dosing on Day 1.

Notes: Percentages are calculated based on the number of subjects in the Safety population per treatment group.

<Laboratory Panel> = Hematology, Chemistry, Urinalysis

Programming Note: X will be assigned as 1, 2, 3 as per laboratory panels.

**Table 14.3.3.2.X.S/M <Laboratory Panel>: Shift Table from Baseline to End of Treatment Results (SAD/MAD)
Safety Population**

Laboratory Parameter (unit)	Study Day [Treatment]	Parameter	Baseline (n=xx)*			
			Low	Normal	High/Abnormal [#]	Total
Parameter 1 (unit)	Day 3/8 [Placebo]	Low	xx (xx.x%)	xx (xx.x%)	xx (xx.x%)	xx (xx.x%)
		Normal	xx (xx.x%)	xx (xx.x%)	xx (xx.x%)	xx (xx.x%)
		High	xx (xx.x%)	xx (xx.x%)	xx (xx.x%)	xx (xx.x%)
		Total	xx (xx.x%)	xx (xx.x%)	xx (xx.x%)	xx (xx.x%)
	Day 3/8 [RP3128 25 mg]			
				

Note: Doses are Total Daily Dose.

Notes: *Baseline is defined as the last observation prior to dosing on Day 1.

[#] For categorical assays, abnormal results are counted under the “High/Abnormal” column (‘Low’ column is ‘N/A’)

Note: Percentages are calculated based on the number of subjects in the Safety population per treatment group.

Note: <Laboratory Panel> = Hematology, Chemistry, Urinalysis

Programming Note: Table will continue for other lab parameters. X will be assigned as 1, 2, 3 as per laboratory panels. For SAD, Day 3 will be used to compare with Baseline. For MAD, Day 8 will be used.

**Table 14.3.4.X.S/M Summary of Vital Signs Data by Treatment, Visit and Time Point (SAD/MAD)
Safety Population
<Vital Signs Parameter (unit)>**

Time Point/ Visit (Day)	Statistic	Pooled Placebo (N=xx)	RP3128 25 mg (N=xx)	RP3128 50 mg (N=xx)	RP3128 100 mg (N=xx)	RP3128 200 mg (N=xx)	RP3128 400 mg (N=xx)
Baseline*	n	xx	xx	xx	xx	xx	Xx
	Mean	xx.x	xx.x	xx.x	xx.x	xx.x	xx.x
	SD	xx.xx	xx.xx	xx.xx	xx.xx	xx.xx	xx.xx
	Minimum	xx	xx	xx	xx	xx	Xx
	Median	xx.x	xx.x	xx.x	xx.x	xx.x	xx.x
	Maximum	xx	xx	xx	xx	xx	Xx
0.5h Day 1							
0.5h Day 1 CFB							
...							

*Baseline is defined as the last observation prior to the dose on Day 1.

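### The laboratory shift table uses one post-dose visit per part, so changes that resolve before it, first appear after it, or precede an early withdrawal are not counted in it

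*SAP*

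**What the plan says.** SAP section 4.1 makes change in clinical laboratory assessments a primary endpoint for both parts. The general rule in section 6.1 is that a "shift table will be produced to present the change of reference range indicator from baseline to post-dose"; no visit is named there.

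Section 9.2.3 names the visit. The 3 by 3 tables run "from baseline to Day 3 for the SAD / Day 8 for the MAD part for each laboratory test". The shell for Table 14.3.3.2 is titled "Shift Table from Baseline to End of Treatment Results (SAD/MAD", and its programming note agrees: "For SAD, Day 3 will be used to compare with Baseline. For MAD, Day 8 will be used".

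The same section sets out the other laboratory displays:

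- change from baseline for quantitative tests at every post-dose visit ("For the SAD part, CFB will be calculated for Day 2, Day 3 (at discharge), Day 8, and Day 15"; in MAD the visits are Days 2, 5, 7, 8 and 15), summarised with mean, SD, median, minimum and maximum;
- category counts ("The reference range indicator data will also be tabulated using frequency and percentage for both quantitative and qualitative results"), which the Table 14.3.3.1 shell lays out separately for baseline and for each study day;
- a full listing by subject and visit, and "Abnormal laboratory findings will also be provided in a separate listing", with an investigator flag for clinical significance.

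No inferential test is planned on laboratory data.

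**The concern.** In a first-in-human dose escalation with no laboratory testing of hypotheses, the descriptive displays are the whole laboratory analysis. The shift table has a particular job among them: it shows who was in range before dosing and out of range afterwards, by dose group and against placebo. Tied to one visit, it does that job only for changes present on that day.

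Three kinds of change fall outside it:

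- those seen earlier and resolved by the chosen visit (Day 2 in SAD; Days 2, 5 or 7 in MAD);
- those first seen later (Days 8 or 15 in SAD; Day 15 in MAD);
- those in subjects who withdraw before the chosen visit and so have no value on that day.

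The third kind has a further consequence. The shell bases percentages on the Safety population of each treatment group, so a subject who withdraws with an abnormal result adds nothing to the numerator and still counts in the denominator. With 3 to 6 active subjects per dose, one subject is a visible part of a group.

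**Working it through.** The plan states no figure to reproduce. The check counts visits and compares what each display can show.

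**Visits** (section 9.2.3; agrees with Table 3 in section 9.2.1)

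| | SAD | MAD |
|---|---|---|
| Post-dose laboratory visits | Days 2, 3, 8, 15 (4) | Days 2, 5, 7, 8, 15 (5) |
| Visit in the shift table | Day 3 | Day 8 |
| Visits outside it | Days 2, 8, 15 (3 of 4) | Days 2, 5, 7, 15 (4 of 5) |
| Of these, after the shift visit | Days 8, 15 | Day 15 |

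**Scheduled subject-visits per test** = subjects × visits, assuming full attendance. Subjects come from the cohort tables in section 3.6.

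- SAD: 4 + 6 + 6 + 8 + 8 = 32 subjects. 32 × 4 = 128 subject-visits, of which 32 × 3 = 96 are outside the table.
- MAD: 8 + 8 + 8 = 24 subjects. 24 × 5 = 120 subject-visits, of which 24 × 4 = 96 are outside the table.

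**Weight of one subject.** Active groups are 3, 4, 4, 6 and 6 in SAD and 6 each in MAD. One subject is 1/3 = 33%, 1/4 = 25% or 1/6 = 17% of a dose group.

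**Effect of withdrawal** (illustration). In a MAD dose group of 6, one subject is normal at baseline, high on Day 5 and leaves before Day 8. If nobody else shifts, the Day 8 table shows 0/6 = 0%. A table over all post-dose results shows 1/6 = 17%.

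**Why the category counts do not replace a shift table** (illustration). Four subjects are Normal, Normal, Normal, High at baseline and Normal, Normal, High, Normal on a later day. Both days show 3 Normal and 1 High, so the counts are unchanged although one subject moved from Normal to High. Change from baseline is a within-subject measure, but it is on the scale of the value, not the category, and it applies to quantitative tests only.

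**Chance shifts under a worst-value table.** Assume, for illustration, that an unaffected subject has a 5% chance of an out-of-range result at any one visit for a given test. Over k visits the chance of at least one lies between 5% (visits perfectly correlated) and 1 − (1 − 0.05)^k (visits independent).

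- SAD, k = 4: 1 − 0.95^4 = 18.5%.
- MAD, k = 5: 1 − 0.95^5 = 22.6%.

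Placebo subjects number 1 + 2 + 2 + 2 + 2 = 9 in SAD and 2 + 2 + 2 = 6 in MAD. The expected chance shifts per test on placebo are then 9 × 0.05 = 0.45 to 9 × 0.185 = 1.7 in SAD, and 6 × 0.05 = 0.3 to 6 × 0.226 = 1.4 in MAD.

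**The case against.** The plan is consistent on this point. Section 9.2.3 and the shell agree, the title presents an end-of-treatment display, and section 6.1 is general enough to contain it. Choosing an end-of-treatment shift over a worst-value shift is a choice of presentation.

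The other displays also cover much of the gap. Change from baseline is summarised at every visit with minimum and maximum, so with 3 to 6 active subjects a single outlier tends to show in a quantitative test. The listings give subject, visit, value and range indicator, so each subject's baseline can be read beside every later result. Section 9.1 names an abnormal laboratory finding as an example of an adverse event, so findings that meet that definition reach the adverse event tables whatever the visit. The shift table is an addition to all this.

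These points stand, and they limit the weight of the concern. They do not remove it. A listing gives no count by dose against pooled placebo, and nothing else in the summary tables crosses baseline category with later category.

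A reader might infer from 3 of 4 and 4 of 5 that 75% of abnormalities in SAD and 80% in MAD would be missed. The documents do not support that. It would require every abnormality to last exactly one visit and to be equally likely at each. The SAP says nothing of the kind, and a change that persists to Day 3 or Day 8 is captured however early it began. If all changes persisted to that visit and none began later, the table would lose none, provided every subject attended it.

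**Conclusion.** The gap is real and limited. One visit per part feeds the shift table, and 3 of 4 (SAD) and 4 of 5 (MAD) post-dose visits do not. What goes uncounted there is a change that resolves before that visit, starts after it, or belongs to a subject who withdraws before it. How many such changes will occur cannot be derived from the SAP, so the size is stated in visits and not in abnormalities.

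It would go too far to say that these results go unreported. They remain in the by-visit summaries, the category counts and the listings. Nor is this an error or a contradiction in the plan. It is a cheap improvement to the display of a primary endpoint, of minor to moderate severity. That judgement rests on the visit schedule in section 9.2, the cohort sizes in section 3.6, and the absence of any other baseline-by-post-dose category table in section 14.

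**What to change.** Add to section 9.2.3 and section 14 a shift table from baseline to the worst post-baseline category, built from all post-dose results, including unscheduled and early-termination results:

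- Show the lowest and the highest post-baseline category separately, since one subject can go out of range in both directions. For tests with only Normal and Abnormal, the second display is enough.
- Present it by dose and for pooled placebo.
- State how many subjects have both a baseline and at least one post-baseline result, so that the percentages can be read correctly.
- Keep the Day 3/Day 8 table as the end-of-treatment display.

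The cost is derived lowest and highest records per subject and test, and one or two more tables per laboratory panel. No new data are needed. The drawback is that taking the worst of several visits raises the number of chance shifts in every group, placebo included. The table should therefore be read against placebo, with the caution that 9 (SAD) and 6 (MAD) placebo subjects make a thin comparison.
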